Annex 2 HCP survey questionnaire

**SURVEY TO EVALUATE THE KNOWLEDGE AND UNDERSTANDING OF THE KEY
SAFETY MESSAGES IN THE HEALTHCARE PROFESSIONAL GUIDE AND THE
PATIENT GUIDE FOR SULIQUA**

- HCP questionnaire -

SURVEY TO EVALUATE THE KNOWLEDGE AND UNDERSTANDING OF THE KEY SAFETY MESSAGES IN THE HEALTHCARE PROFESSIONAL GUIDE AND THE PATIENT GUIDE FOR SULIQUA

Section 1: Screener

S1. Are you currently employed by a pharmaceutical company or contracted by regulatory bodies (e.g. EMA = ZVA, Hungary = OGYEI, Italy = AIFA, Czech Rep =SUKL, Slovenia =JAZMP)?

1	No	()
2	Yes	()

Data: single punch

If S1=2 then THANK&CLOSE

S2. Have you ever prescribed / dispensed Suliqua?

1	Yes	()
2	No	()

Data: single punch

If S2=2 then THANK&CLOSE

S3. Approximately how many patients have you treated with /delivered Suliqua in the last 3 months?

.....

Data: Open numeric 0-500

If 0 => STOP then THANK&CLOSE

If >0 => continue

Section 2: HCP Practice information

D1. For how many years have you been working with patients with diabetes?

1	≤ 5 years	()
2	6 to 10 years	()
3	> 10 years	()

Data: single punch

D2a. What is your main medical specialty?

1	General practice (GP)/ family physician	()
2	Endocrinology/ Diabetology (Medical doctors or nurse practitioners)	()
3	Pharmacist	()
4	Internist	()
5	Gastroenterologist	
6	Geriatrics	
7	Other	()

Data: single punch

If D2=7 then THANK&CLOSE

(For UK questionnaires: Replace " Internist" by "Internal Medicine"; remove Gastroenterologists in UK as they do not prescribe antidiabetic drugs)

D2b. For how long have you been working in this specialty?

For |_|_| years

Data: open numeric, 2 digits

D3. In which type of setting do you work in? (you can select more than one answer)

1	Office	()
2	Hospital	()
3	Diabetes care clinic	()
4	Community Pharmacy	()
5	Hospital Pharmacy	()

Data: multiple punch

If D2a = 1,2,4,5 then ask i1,i2,i3

If D2a = 3 then ask i4,i5

(For UK: in the UK the term "Office" is not used: would rephrase to "Private Practice")

Section 3: Prescribing conditions and safety information/warnings of Suliqua 10-40 or 30-60 pen

Explanatory text

Please answer the following general questions about the prescribing conditions and safety information of Suliqua

Q1. Which educational materials (EM) related to Suliqua have you received ?

1	Guide for Healthcare professionals	 Yes  No  I do not remember
2	Guide for patients and/or caregivers	 Yes  No  I do not remember
3	Letter - Important prescribing information	 Yes  No  I do not remember

Data: single punch per row

Ask Q2a only if response to 1 is yes

Ask Q2b only if response to 2 is yes

Key message:

Sanofi should deliver educational material to Healthcare professionals according to the additional risk minimization measures described in the Suliqua Risk Management Plan.

Q2a. Please answer to the following questions related to the use of the Guide for Healthcare Professionals:

	Use of educational materials	
1	Do you review the HCP guide checklist when prescribing/dispensing Suliqua to a patient for the first time ?	 Never  Occasionally  Frequently
2	Do you review the HCP guide checklist when changing Suliqua pen strength to a patient for the first time ?	 Never  Occasionally  Frequently
3	Do you review each point of the checklist?	 Never  Occasionally  Frequently

Data: single punch per row

Key message:

HCPs should review the checklist that is in the guide to Healthcare professional when you prescribe /deliver Suliqua pens.

Q2b. Please answer to the following question related to the use of the Guide for patients and/or caregivers:

	Use of educational materials	
	Do you provide patients with patient guide prior initiating Suliqua	 Never  Occasionally  Frequently

Data: single punch per row

Key message:

HCPs should provide patients with the patient guide prior to prescribing or dispensing Suliqua.

Q3. According to your knowledge about the dose titration of Suliqua, which of the following statements are true and which are false?

	Prescription /Patient first daily dose/ dosage titration	TRUE	FALSE
1	Insulin-naive patients (on oral antidiabetic only), should start with 10 dose steps daily.	()	()
2	Patients who received between 20 and 30 units of insulin, should start with 30 dose steps daily.	()	()
3	Patients who received insulin or insulin glargine twice a day, should have a reduction of total daily dose of Suliqua by 10%.	()	()
4	For doses >40 dose steps/day titration must be continued with Suliqua (30-60) pen.	()	()
5	For total daily doses >60 dose steps/day, Suliqua must not be used.	()	()

Data: single punch per row

Answer:

Option 2 is wrong (patient had insulin before between 20 and 30 units, patient should start with 20 dose steps

Option 3 is wrong (Patients who received insulin or insulin glargine twice a day, should have a reduction of total daily dose of Suliqua by 20%)

Key message:

Prescriber /Pharmacist should understand and know the table in HCP guide for starting dose

Q4. According to your knowledge about the two different Suliqua pens, which of the following statements are true and which are false?

	Prescription/ Pen choice	TRUE	FALSE
1	Patient can use the colour of pen of his/her choice	()	()
2.	The Suliqua (10-40) pen allows a daily injection of doses between 10 and 40 dose steps	()	()
3	The Suliqua (30-60) pen allows a daily injection of doses between 30 and 60 dose steps	()	()
4	The Suliqua pen (30-60) is olive coloured with a brown button	()	()
5	Both pre-filled pens contain insulin glargine in a strength of 100 Units/mL	()	()

Data: single punch per row

Answer:

Option 1 is wrong (patient should use the pen according to the dose steps that he/she will be prescribed).

Key message:

Prescriber /Pharmacist should understand and know the table in HCP guide for starting dose

Q5. According to your knowledge related to the communication with the patients, what important message(s) should be provided to the patient? (you can select more than one answer)

	Education of patient	
1	Patients should use the same needle for several injections	()
2	Patients should closely monitor their blood sugar level when starting Suliqua which contains insulin glargine 100U/ml and lixisenatide (non insulin substance)	()
3	The dose pointer shows the number of dose steps to be injected	()
4	Patients should read the patient guide and the patient information leaflet, as well as the leaflet provided in Suliqua Solo Star packaging carefully.	()
5	Patients who are blind or have low vision should be helped by another person who has been trained on Suliqua use	()
6	The peach colour pen and the olive colour pen contain the same concentration of insulin	()
7	Patients should report any side effect/medication error to their doctor or pharmacist	()

Data: multiple punch

Option 1 incorrect

Key message:

HCP should refer to the HCP material and checklist to inform patient about specificities of the pen use.

Q6. According to your knowledge what should be the important information to be indicated in the prescription for Suliqua? (you can select more than one answer)

	Prescription	
1	Number of dose steps to be injected	()
2	Strength of pen	()
3	Name of product	()
4	Associated dose range /strength	()

Data: multiple punch

Answer: mandatory: 1,3,4;

Key message

The prescription should mention which pre-filled pen type you need (the SULIQUA [100 units/mL + 50 micrograms / mL] pen or the SULIQUA [100 units/mL + 33micrograms / mL] pen) and the number of dose steps to be injected.

Q7. According to your knowledge, which of the following Suliqua safety messages should be communicated to patients treated with Suliqua ? (you can select more than one answer)

	Safety messages	
1	Patients may experience side effects and should talk to their doctors or pharmacists	()
2	Patients may develop osteosarcoma and should be monitored for bone pain and swelling	()
3	Medication errors are the most common cause of adverse events and patients should ask, if needed, clarifications on how to use their pen and on how many dose steps they require	()

4	Patients may experience dysglycemia and should measure their blood sugar more frequently in the weeks after the shift to Suliqua	()
---	--	-----

Data: multiple punch

Answer: Option 2 is wrong

Key message:

HCPs should explain that the patient should anticipate dysglycemia and potential adverse reactions.

Q8. According to your experience, which of the following are the most relevant sources of information that should guarantee appropriate use of Suliqua by patients? (you can select more than one answer)

	Source of information	
1	Patient guide	()
2	Patient leaflet and instructions for use accompanying the pen	()
3	Explanations from prescribing physician	()
4	Explanations from delivering pharmacist	()
5	Explanations from a nurse	()
6	Other (ie: Patient group experience, internet, ..)	()

Data: multiple punch

Q9 and Q10 for prescribers [D2a=1 or 2 or 4 or 5]

Q9. How many prescriptions for Suliqua have you been queried about or have been returned for clarification by dispensers / pharmacists in the last 3 months?

1	None (0)	()
2	1-5	()
3	6-10	()
4	11-20	()
5	>20	()

Data: Single punch

Q10 How many prescriptions for Suliqua have you been queried about or have you been asked for clarification by patients in the last 3 months?

1	None (0)	()
2	1-5	()
3	6-10	()

4	11-20	()
5	>20	()

Data: Single punch

Q9 and Q10 for dispensers [D2a=3]

Q9 How many prescriptions for Suliqua have you been queried about or returned for clarification by the prescriber in the last 3 months?

1	None (0)	()
2	1-5	()
3	6-10	()
4	11-20	()
5	>20	()

Data: Single punch

Q10 How many prescriptions for Suliqua have you been queried about for clarification by patients in the last 3 months?

1	None (0)	()
2	1-5	()
3	6-10	()
4	11-20	()
5	>20	()

Data: Single punch

Another survey will be conducted to assess the knowledge and understanding of the key safety messages in the Patient Guide among patients treated with Suliqua. Would you like to help us, by giving the survey questionnaire to your patients? They will then complete an online/paper questionnaire anonymously without your involvement. You will be paid: **XX € / completed patient/caregiver questionnaire. IQVIA will re-contact you in order to make the necessary arrangements for patient survey distribution.**

1. Yes, I would like to distribute the patient survey among my patients. I agree to be contacted again for this purpose.
2. No

Data: Single punch

If yes, display :

1. I would like to be contacted by IQVIA using the default contact information
2. I would like to provide different contact information

Data: Single punch

If item 2 selected then show:

Please confirm your details:

YOUR NAME:	
E-MAIL ADDRESS:	
ADDRESS:	

Note:

Blue is for data and will not appear in questionnaire,

Green is for internal use and will not appear in questionnaire,

Black will be in the questionnaire.

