9 RESEARCH METHODS

9.1 STUDY DESIGN

This survey will be cross-sectional, multinational, multichannel and conducted among HCPs as well as patients/caregivers in 3 waves.

There will be two questionnaires, one designed for the HCPs and another designed for patients/caregivers. These questionnaires include the following sections:

Table 1: Sections of HCP's and patient's questionnaires

HCP Questionnaire	Patient/Caregiver Questionnaire
Screening section (items S1-S3)	Screening section (items S1-S2)
HCP practice information (items D1-D3)	Questionnaire (items S3-S6, Q1-Q7)
Prescribing/delivery conditions and safety information (items Q1-Q10)	

The survey will be conducted primarily through a web questionnaire. Paper questionnaires will be additionally proposed to patients and phone questionnaires to HCPs who would not be able to answer the survey online.

In each country, HCPs will be identified according to their specialty (general practitioners [GP], endocrinologist/diabetologist, internists, gastroenterologists, pharmacists, nurse, geriatrists) as specified in OneKey lists (IQVIA). OneKey is the most comprehensive worldwide database of HCPs. It is constructed according to ISO 9001: 2015 Quality Management Systems Requirements. The lists are representative of the HCPs population in the selected countries.

For patients recruitment, HCPs to be contacted will be randomly selected according to the procedure described in the sampling plan section (Section 9.2.4). They will be sent patient kits for distribution to the patients.

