9.2.4 Modalities of recruitment

9.2.4.1 HCP selection

HCPs will be identified from OneKey lists. A random stratified sampling method will be applied. As a first step, all lists will be merged, and then the eligible HCPs will be divided into homogeneous

groups, called strata, which are mutually exclusive (an HCP can only belong to one stratum). This stratification will be based on the following criteria:

Number of strata formed = number of countries * number of specialties

In order to fill-in each stratum of the sample survey from the IQVIA OneKey reference files, an independent sample will be selected per stratum through a simple random sampling without replacement.

In each specific stratum, HCPs will be contacted according to the order of draw in this stratum. If an HCP does not want to participate in the survey, the next one in order of draw will be contacted, and so on until the required number of HCPs is met. If the target for a stratum is not achieved after the end of the initial list, an additional randomly sampled list will be prepared, and the HCPs contacted until the goal is reached or no names are left in that stratum. If the complete list of the IQVIA OneKey reference files has been exhausted in any particular stratum, a strategy will be determined to adjust the sample size within stratum with associated weighting.

In web surveys, the number of HCPs to be contacted for reaching the required number of HCPs with analysable questionnaires is usually around ten times more than the expected final number.

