9.3.1 Collected/estimated through the HCP questionnaire

- Information related to HCPs/patients participation: contact rate, response rate, cooperation rate, and refusal rate (section 9.7)
- Variables related to HCPs practice information:
 - Duration of practice (year working with diabetic patients)
 - Specialty (GP, endocrinologist/diabetologist, pharmacist, internist, gastroenterologist, nurse, geriatrist)
 - Type of setting (office based, hospital based, both, outpatient pharmacy, hospital pharmacy, diabetes care clinic)

- Past experience with SULIQUA (number of patients treated with SULIQUA pre-filled pen)
- Variables related to the HCPs knowledge about the prescribing conditions and safety information/warnings of SULIQUA data include:
 - HCP knowledge about SULIQUA pre-filled pen guide for HCPs
 - Awareness of the responsibility to provide each patient with the guide for patient treated with SULIQUA
 - Knowledge of the instructions for appropriate utilization of SULIQUA pre-filled pen (dose titration, pen choice, storage, adverse reactions e)
 - Appropriate labelling of dose range and strength of SULIQUA pre-filled pen and dose steps to be administered in prescription (yes/no)
 - Education/Advice of the patient with regard to dose steps required, design features and appropriate utilization of SULIQUA pre-filled pen, close blood sugar levels monitoring after initiation, safety information
 - Number of recorded medication errors since EM distribution
- Receipt of SULIQUA pre-filled pen guide for HCPs (yes/no)
- Distribution to patients/caregivers of the guide for patient treated with SULIQUA (yes/no)

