9.7 DATA ANALYSIS

The statistical analyses will be described and further detailed into a Statistical Analysis Plan (SAP). The described analysis below might be revised, and adjustments might occur. The final SAP version will include (empty) table shells to be populated for the clinical study report (CSR).

General considerations:

The statistical analysis will be conducted using the SAS[®] software V9.4 on Windows[™] (SAS Institute, North Carolina, US).

Continuous variables will be described by their number (of valid cases, of missing values), mean, standard deviation, median, Q1, Q3, minimum and maximum. Categorical variables will be described as the total number and relative percentage per category. Confidence intervals of 95% will be evaluated, when relevant. The number of missing data will be indicated. Since, missing values are expected to be few and distributed at random, no replacement or imputation will be performed. Missing values will not be considered in the denominators for proportions.

For HCP questionnaire measures, results will be stratified by country and physician's specialty. For patient questionnaire measures, results will be stratified by country and treating physician's specialty. In tables "Overall - unweighted" columns and lines will show the results observed on the sample while "Overall weighted" columns and rows will show the results weighted according to the distribution of HCPs in the general population by country and specialty, respectively.

Two interim and 1 final analysis corresponding to 3 waves of survey will be performed according to timelines (Section 6) in selected European countries.

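### Nurses and geriatricians are listed specialties and sampling strata, but the HCP questionnaire gives nurses no separate code and never routes geriatricians to D3, Q9 or Q10

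*Protocol*

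**What the plan says.** Protocol section 9.1 identifies HCPs by specialty from the OneKey lists, and the list ends with "gastroenterologists, pharmacists, nurse, geriatrists". Section 9.2.4.1 sets the strata: "Number of strata formed = number of countries * number of specialties". Section 9.3.1 makes specialty a variable obtained through the HCP questionnaire, with seven levels: "Specialty (GP, endocrinologist/diabetologist, pharmacist, internist, gastroenterologist, nurse, geriatrist"; section 9.6.3.1 repeats them. Section 9.7 reports by specialty: "For HCP questionnaire measures, results will be stratified by country and" specialty, with weighted and unweighted totals. Section 9.7.2 gives participation rates on the same breakdown.

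In Annex 2, specialty is collected by D2a. Its options are general practice, endocrinology/diabetology (worded to cover medical doctors and nurse practitioners), pharmacist, internist, gastroenterologist, geriatrics and other. Code 7 ends the interview: "If D2=7 then THANK&CLOSE". Setting (D3) is routed by "If D2a = 1,2,4,5 then ask i1,i2,i3", with a second line for code 3. The prescription-query items are headed "Q9 and Q10 for prescribers [D2a=1 or 2 or 4 or 5" for prescribers and are otherwise shown only to dispensers with code 3.

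**The concern.** The sampling plan and the instrument use different specialty lists. A nurse drawn from a nurse stratum has no matching answer at D2a. Outside code 2, the accurate choice is Other, which closes the survey. This is not an eligibility screen working as intended. S2 (ever prescribed or dispensed) and S3 (more than zero patients in the last three months) come before D2a, so a nurse closed out there has already met the only HCP inclusion criterion in section 9.2.2.1. No exclusion in section 9.2.2.2 concerns nurses.

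Geriatricians do have a code, but the routing lines omit it. Type of setting is one of the characteristics section 9.7.1 uses to profile HCPs with incorrect answers, and Q9/Q10 are the only items on prescription queries. Section 9.7 justifies no imputation by expecting missing values to be sparse and random. For geriatricians, absence on these items is complete and determined by specialty. A later analysis plan cannot recover questions that were never asked or interviews that were ended.

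**Working it through.** **Trace of each D2a code through the Annex 2 routing**

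| Code | Option | After D2a | D3 options shown | Q9/Q10 version |
|---|---|---|---|---|
| 1 | General practice | continues | 1–3 | prescriber |
| 2 | Endocrinology/diabetology, including nurse practitioners | continues | 1–3 | prescriber |
| 3 | Pharmacist | continues | 4–5 | dispenser |
| 4 | Internist | continues | 1–3 | prescriber |
| 5 | Gastroenterologist (removed in the UK) | continues | 1–3 | prescriber |
| 6 | Geriatrics | continues | none | none |
| 7 | Other | terminated | – | – |

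Of the seven listed specialties, six have their own code (all but nurse) and five have both a code and full routing (all but nurse and geriatrist).

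**Cells affected**, assuming every listed specialty is sampled in every country:

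- Wave 1 (Czech Republic, Hungary, Slovenia): 3 × 7 = 21 strata. Nurse and geriatrician cells: 3 × 2 = 6, so 6 of 21.
- Wave 2 (Belgium, Croatia, Romania, United Kingdom): 4 × 7 = 28, less the UK gastroenterologist cell that Annex 2 removes, gives 27. Nurse and geriatrician cells: 4 × 2 = 8, so 8 of 27.
- If Croatia, which the protocol calls at risk, drops out of Wave 2: 3 × 7 − 1 = 20 strata, of which 6 are affected.

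**Success factors.** Section 9.7.1 builds the three HCP factors from Q1; from Q3, Q4 and Q7; and from Q2a, Q2b, Q5 and Q6. No D2a routing line withholds any of these from code 6. Q9, Q10 and D3 enter none of them.

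**Sample size, as background.** The plan's figures reproduce: 0.25 × 1.96² / 0.05² = 384; 1.96 × √(0.25/128) = 8.66%; 128/0.85 = 150.6, stated as 150. The nurse share is not stated, so the loss of precision can only be illustrated. Suppose nurses are 2% to 20% of the 150 HCPs in a wave, all answer Other and none is replaced:

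- 2%: 3 lost; 147 × 0.85 = 125 analysable; half-width 8.8%.
- 20%: 30 lost; 120 × 0.85 = 102 analysable; half-width 9.7%.

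Replacement from other strata would restore the number but not the nurse stratum.

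**The case against.** Five points can be made on the other side.

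- **Nurses are not shut out as a group.** A reader might infer that the survey excludes them all. Code 2 admits diabetes nurse practitioners and gives them D3, Q9 and Q10. S2 and S3 first remove nurses who do not prescribe or dispense. Since D2a asks for a main specialty, a nurse in general practice or geriatrics might choose code 1 or 6. This stands: the terminated group is eligible nurses who answer Other, and its size is unknown. It does not remove the defect, because nurses in codes 1, 2 or 6 cannot be told apart from physicians in D2a.
- **Weights.** It is tempting to conclude that nurses in code 2 get the wrong stratum weight. The documents do not support that. Specialty for sampling comes from OneKey (section 9.1), strata are drawn before any answer is given (section 9.2.4.1), and section 9.5.2 weights back to the reference lists. Nothing says D2a overrides the sampled stratum. Nothing says the reverse either, so the source should be stated.
- **Effectiveness criterion.** A reader might think the geriatrician stratum is lost to the main result. It is not: those respondents answer every success-factor item. What they lack feeds descriptive output.
- **Missing data.** An item withheld by routing differs from item non-response, and leaving it out of the denominator does not distort other specialties' results. That is fair, but it is a reason to label the items as not asked.
- **Reporting rows.** Mock Table 4 has no nurse or geriatrician row, only Other. The template is declared provisional, so the reporting commitment rests on the text of sections 9.3.1, 9.7 and 9.7.2.

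**Conclusion.** The mismatch is plain in Annex 2 and the instrument is wrong as written. One declared specialty cannot be identified from D2a, and some of its eligible members may be terminated. Another, geriatrics, is missing in full on three items. In cells this is 6 of 21 in Wave 1 and 8 of 27 in Wave 2, given all listed specialties in every country apart from UK gastroenterologists. These counts describe reach, not effect: the protocol gives no nurse or geriatrician allocation, so the consequence for overall estimates cannot be stated. The geriatrician conclusion assumes that the routing was programmed as printed. The geriatricians' contribution to the effectiveness criterion is unaffected. The point is worth correcting because the lost answers cannot be recovered later and the correction is small.

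**What to change.** For Wave 3 and any Wave 2 country not yet fielded, add a Nurse option to D2a with D3 and Q9/Q10 routing, and add code 6 to the D3 and prescriber Q9/Q10 routing. Reconcile the specialty list in the protocol text with Annex 2.

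For data already collected:

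- State that analysis stratum and weight come from the OneKey sampling specialty wherever the response can be linked to it.
- Report the number closed out at D2a code 7, by OneKey specialty.
- Show D3, Q9 and Q10 for geriatricians as not asked, separately from missing.

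The cost is one translated answer label, a small web and phone reprogramming job, and a recode of existing data. Section 9.8.1 stores identifying information apart from the answers, so the link to OneKey may not always be available. The code list may also differ between waves. Section 6 planned Wave 2 collection from 01 January 2020, before the amendment dated 24 February 2020 in the document history. If Wave 2 is already in the field, the list may differ within that wave too, and the report should say so.

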9.7.1 Primary analysis

Distribution of all possible answers

As some questions may have multiple choices or be opened fields, the proportion of HCPs/patients having provided each possible answer will be described (Table 4).

Table 4: Mock table: Distribution of HCPs/patients answers to Question XX by country and physician specialty

Specialty	Answer	Country			Overall unweighted n(%)	Overall weighted * %
		Country 1 (N=XX)	Country 2 (N=XX)	...		
GP (N=XX)	Answer 1	xx (xx.xx)	xx (xx xx)	xx (xx xx)	xx (xx xx)	xx xx
	Answer 2	xx (xx.xx)	xx (xx xx)	xx (xx xx)	xx (xx xx)	xx xx
	...	xx (xx.xx)	xx (xx xx)	xx (xx xx)	xx (xx xx)	xx xx
	Missing	xx	xx	xx	xx	-
Endocrinologist (N=XX)	...	xx (xx.xx)	xx (xx xx)	xx (xx xx)	xx (xx xx)	xx xx
Internist (N=XX)	...	xx (xx.xx)	xx (xx xx)	xx (xx xx)	xx (xx xx)	xx xx
Gastroenterologist (N=XX)	...	xx (xx.xx)	xx (xx xx)	xx (xx xx)	xx (xx xx)	xx xx
Other (N=XX)	...	xx (xx.xx)	xx (xx xx)	xx (xx xx)	xx (xx xx)	xx xx
Overall unweighted (N=XX)	Answer 1	xx (xx.xx)	xx (xx xx)	xx (xx xx)	xx (xx xx)	xx xx
	Answer 2	xx (xx.xx)	xx (xx xx)	xx (xx xx)	xx (xx xx)	xx xx
	...	xx (xx.xx)	xx (xx xx)	xx (xx xx)	xx (xx xx)	xx xx
	Missing	xx	xx	xx	xx	-
Overall weighted	Answer 1	xx xx	xx xx	xx xx	xx xx	xx xx
	Answer 2	xx xx	xx xx	xx xx	xx xx	xx xx
	...	xx xx	xx xx	xx xx	xx xx	xx xx

* According to the distribution of HCPs in the general population by country and specialty, respectively.

Note: This template might be modified, final table shells will be presented in the statistical analysis plan (SAP).

Definition of success

Three success factors for professionals treating patients with SULIQUA will be defined:

1. Proportion of HCPs receiving the EMs (Question Q1 of HCP questionnaire).
2. Proportion of HCPs sufficiently understanding the key messages, i.e. providing at least 75% of correct answers (Questions Q3-Q4, Q7 of HCP questionnaire; at least 11 correct or consistent answers out of 14 sub-questions).
3. Proportion of HCPs adequately implementing the EMs, i.e. providing at least 75% of answers that are correct or consistent with appropriate use of the EMs (Questions Q2a-b, Q5-Q6 of HCP questionnaire; at least 12 correct or consistent answers out of 15 sub-questions).

Three success factors for patients/caregivers will be as follows:

1. Proportion of patients/caregivers receiving the EM (Question Q5 of Patient/Caregiver questionnaire).

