9.8 QUALITY CONTROL

9.8.1 Data collection, validation and data quality control at IQVIA level

Data will be collected using a web or paper questionnaire.

The survey will be conducted according to the Standard Operating Procedures (SOPs) of IQVIA Primary Intelligence and IQVIA Real World Evidence Solutions.

For web version of the questionnaires, data will be collected using an electronic data capture system developed following a full validation process. A rigorous System Development Life Cycle (SDLC) is used for validation that complies with internal IT SOPs of Primary Intelligence (IQVIA). Unit testing and formal validation occur on all appropriate systems and components during the build stage. The SDLC is fortified with SOPs addressing validation for all clinical and risk management-related applications. The internet-based repository will be used to store survey data and, other relevant program information. Questions are programmed to ensure that they are asked in the appropriate sequence. Skip patterns are clearly indicated. Respondents cannot go back to a question once the question has been answered and they cannot skip ahead. Response options presented in a list are randomized to minimise positional bias. Programming will be reviewed by quality control and simulated users (User Testing) prior to implementation.

For the paper questionnaire, respondents will be asked to complete questionnaire thoroughly with a ball-point pen and will be informed that responses modified (deletion, overprint) by participants will be considered as missing. Questions will be ordered in a way that no response to one question is available later in the questionnaire. The questionnaire will use multiple visual elements together to improve skip pattern compliance.

Collected data will be entered and stored in a database specific to the survey and the country. A study database will be created by the merging of databases of each country. HCP identifying information will be stored separately from survey data.

Data will be checked in terms of consistency before data analysis:

- Removal of duplicates (if required)
- Data labelling and data formatting
- Range and consistency checks for each variable to identify potential non admissible values
- Cross-check the consistency of data for related variables (if feasible)

The study database will be locked once validated.

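### HCP Q2a item 2 scores checklist review at a pen-strength change but offers no 'not applicable' answer, so HCPs who have never changed a pen tend to lose a factor 3 point (minor)

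*Protocol*

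**What the plan says.** - **The item.** Protocol Annex 2, Q2a item 2: "Do you review the HCP guide checklist when changing Suliqua pen strength to a patient for the first time". The answers offered are "Never Occasionally Frequently". There is no 'not applicable' and no 'I do not know'.
- **Routing.** The only condition is "Ask Q2a only if response to 1 is yes", where row 1 of Q1 is receipt of the HCP guide. Experience of a pen change is not asked about.
- **Screening.** S3 asks "Approximately how many patients have you treated with /delivered Suliqua in the last 3 months" and closes the interview only if the answer is zero. One recent patient is enough.
- **Scoring.** Section 9.7.1 defines HCP success factor 3 as "providing at least 75% of answers that are correct or consistent with appropriate use of the EMs" and makes it concrete as "Questions Q2a-b, Q5-Q6 of HCP questionnaire; at least 12 correct or consistent answers out of 15 sub-questions".
- **Decision rule.** Under section 9.7.1 the measures count as effective for HCPs if at least two of the three factor proportions reach 80%.
- **Unanswered items.** Section 9.8.1 says of the web form: "Respondents cannot go back to a question once the question has been answered and they cannot skip ahead". Section 9.7.2 accepts submitted HCP questionnaires with some answers missing. Section 9.7 leaves missing values out of the denominators of proportions. None of the three says how a blank enters the 15-item score.

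**The concern.** Item 2 has a clear meaning only for an HCP who has moved a patient from one pen to the other. An HCP who reviews the checklist at every start but has not yet met a change of pen has no option that is both accurate and credited. The Q2a key message expects HCPs to go through the checklist when prescribing or delivering the pens, so Never reads as the unfavourable answer. Factor 3 would then record a missing opportunity as a failure to implement.

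The plan presents success by country and profiles HCPs with incorrect answers by country, specialty and past experience. If HCPs differ in how often they change pens, part of a difference in factor 3 would be a difference in switching volume. No other HCP question records whether a pen was ever changed (S3 counts patients only), so the two kinds of Never cannot be told apart once the data are in, whatever scoring rule is used.

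**Working it through.** **1. Reproduce the plan's count and pass mark.** From Annex 2, Q2a has 3 items, Q2b 1, Q5 7 and Q6 4: 3 + 1 + 7 + 4 = 15. The 75% rule gives 0.75 × 15 = 11.25, rounded up to 12. Both figures agree with section 9.7.1, and 15 is reached only if Q2a item 2 is scored.

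**2. Requirement for an affected HCP.** Take an HCP who received both guides, has never changed a pen and answers Never.
- As written: 12 of the other 14 items, 12/14 = 85.7%, against 12/15 = 80% for an HCP to whom every item applies. Two misses are allowed among the 14, instead of three among the 15.
- With the item taken out of the score: 0.75 × 14 = 10.5, rounded up to 11, and 11/14 = 78.6%.

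**3. Effect on the chance of passing.** The protocol gives no per-item success rate, so *p* is assumed equal across items, with independent items. The chance of passing is the exact binomial tail P(X ≥ k | n, p).

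| p per item | All items apply, 12 of 15 | Item 2 answered Never, 12 of 14 | Item 2 removed, 11 of 14 |
|---|---|---|---|
| 0.80 | 0.648 | 0.448 | 0.698 |
| 0.85 | 0.823 | 0.648 | 0.853 |
| 0.90 | 0.944 | 0.842 | 0.956 |
| 0.95 | 0.995 | 0.970 | 0.996 |

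**4. Effect on the factor 3 proportion.** Let *s* be the share of all HCPs who were asked Q2a, hold both guides, have never changed a pen and answer Never. It is not in the protocol. The fall is *s* × (column 2 − column 3).

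| p | Difference | s = 10% | s = 30% | s = 50% |
|---|---|---|---|---|
| 0.80 | 0.200 | 2.0 points | 6.0 | 10.0 |
| 0.85 | 0.175 | 1.8 | 5.3 | 8.8 |
| 0.90 | 0.102 | 1.0 | 3.1 | 5.1 |
| 0.95 | 0.025 | 0.3 | 0.8 | 1.2 |

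**5. Can it cross the 80% line?** At p = 0.85 and s = 30%, factor 3 as written is 0.7 × 0.823 + 0.3 × 0.648 = 0.770. With the item removed for those HCPs it is 0.7 × 0.823 + 0.3 × 0.853 = 0.832. Of that gap, 0.823 − 0.770 = 5.3 points come from the uncredited item and 0.832 − 0.823 = 0.9 from the easier rounding of 11 of 14. At s = 10% the two values are 0.805 and 0.826, both above the line. At p = 0.90 both stay above 80% for every share shown (0.893 and 0.950 at s = 50%).

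**The case against.** **The forced answer.** A reader might infer that an HCP without a pen change can answer only Never. The documents do not support that. The question is put in the habitual present, so it can be answered by intended practice. A blank may also be possible, since section 9.7.2 allows missing answers while section 9.8.1 bars skipping ahead on the web. These routes do not repair the item: a hypothetical answer mixes intention with behaviour, and the treatment of a blank in the score is not stated.

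**The lost point.** Annex 2 prints answer keys for Q3 to Q7 but none for Q2a. The loss is inferred from the key message, and a statistical analysis plan that is not shown may set the scoring. It could not, however, recover who had never changed a pen.

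**Who is affected.** A reader might also infer that pharmacists as a group cannot answer. The Q2a key message covers delivery as well as prescribing, so a pharmacist dispensing a new strength can read the item as applying. S3 sets an entry floor and says nothing about how common pen changes are. Section 9.2 selects countries where both pens have been marketed for at least six months, which limits the argument from recent launch.

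**Size and consequence.** Any single figure is one cell of an assumed grid. It concerns only HCPs who were asked Q2a, and it assumes independence although the three Q2a habits are probably correlated. Factor 3 tolerates three misses, and the verdict needs only two of three factors. The bias runs against declaring success. Section 9.7.1 also tabulates every answer, so the share answering Never will be seen. All of this stands and keeps the point small. The tabulation shows the total of Never answers but not its composition.

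**Conclusion.** The point holds as a minor flaw in the questionnaire. Item 2 is scored, has no answer for HCPs to whom it does not apply, and no screener or routing keeps those HCPs out. The likely bias in factor 3 is downward. Under independent items and an affected share of 10% to 50% of all HCPs, it ranges from about 0.3 to 1.2 points at 95% correct per item up to 2 to 10 points at 80%. Both inputs are assumptions, and so is the reading that Never earns no credit. The conclusion on effectiveness changes only if factor 3 lies near 80% and is the factor that decides the two-of-three rule.

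**What to change.** - **Any wave or country not yet fielded:** add to Q2a item 2 the option *Not applicable: I have not changed a patient's pen strength*. For HCPs choosing it, score factor 3 as at least 75% of the remaining items (11 of 14 with both guides).
- **Waves already fielded, and comparison across waves:** report factor 3 with item 2 left out for all HCPs (at least 11 of 14) as a sensitivity analysis beside the planned result. By section 6, data collection for Waves 1 and 2 was scheduled to start before the amendment date of 24 February 2020, so for much of the study this is the available remedy.

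**Cost.** One answer option has to be translated and back-translated, and comparability with fielded waves is slightly reduced. Rounding makes 11 of 14 (78.6%) a little easier than 12 of 15 (80%): in the first table of the working the gain is 0.698 − 0.648 = 5.0 points at p = 0.80, 3.0 at 0.85, 1.2 at 0.90 and 0.1 at 0.95. The report should say so, so that a gain of that order is not attributed to item 2.
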